1.1. Synopsis

Protocol Title:

A Phase 2, Randomized, Double-Blind, Placebo-Controlled Study to Investigate the Efficacy and Safety of LY3819469 in Adults with Elevated Lipoprotein(a)

Brief Title:

Efficacy and safety of LY3819469 compared with placebo in adults with elevated Lp(a)

Regulatory Agency Identifier Number(s):

IND: 154938

EU trial number: 2022-501426-38-00

Rationale:

Elevated lipoprotein(a) (Lp[a]) is recognized as an important risk factor for cardiovascular disease; there are currently no approved pharmaceutical interventions for lowering Lp(a). LY3819469 is a novel Dicer-substrate small interfering ribonucleic acid (siRNA) oligonucleotide designed to reduce the levels of LPA mRNA and apolipoprotein(a) (Apo[a]) expression and thereby to decrease Lp(a). In Phase 1 Study J3L-MC-EZEA, single subcutaneous (SC) doses of LY3819469 significantly and durably decreased Lp(a) and no safety issues were identified. This Phase 2 study aims to investigate the impact of a range of LY3819469 doses on Lp(a) level and on safety in a larger population of participants with elevated Lp(a) to enable Phase 3 development of this compound.

Objectives, Endpoints, and Estimands:

Objectives	Endpoints
Primary	
• To evaluate if LY3819469 is superior to placebo in percent Lp(a) reduction	 Percent change from baseline in time-averaged Lp(a) over Days 60- 180
Secondary	
• To evaluate if LY3819469 is superior to placebo in percent Lp(a) reduction over Days 240-360	 Percent change from baseline in time-averaged Lp(a) over Days 240- 360
• Compare proportion of participants on LY3819469 versus placebo achieving Lp(a) threshold levels	 Proportion of participants achieving Lp(a) <125 and <75 nmol/L at Days 60, 180, 240, 360, and 540

Objectives	Endpoints
• Compare the effect of LY3819469 to placebo on cardiovascular biomarkers	 Percent change from baseline to Days 60, 180, 240, 360, and 540 for Lp(a) ApoB hsCRP
Characterize the PK of LY3819469	Population PK parameters

Abbreviations: ApoB = apolipoprotein B; hsCRP = high-sensitivity C-reactive protein; Lp(a)_= lipoprotein(a); PK = pharmacokinetics.

Estimands

The primary clinical question of interest is: What is the study intervention difference in percent change from baseline in time-averaged Lp(a) over Days 60-180 of study intervention in participants who meet the enrollment criteria regardless of treatment discontinuation for any reason?

A similar estimand as the estimand for the primary objective will be used for the secondary objectives.

Unless specified otherwise, safety assessments will be guided by an estimand comparing safety of LY3819469 doses with placebo irrespective of adherence to study intervention.

Overall Design

Study is a parallel, double-blinded, placebo-controlled, dose-finding, Phase 2 study of LY3819469 in participants with elevated Lp(a).

Approximately 254 participants will be randomized in a 1:2:2:2:2 ratio to 1 of the following arms:

- Arm A: 16-mg LY3819469, doses at randomization and Day 180
- Arm B: 96-mg LY3819469, doses at randomization and Day 180
- Arm C: 400-mg LY3819469, doses at randomization and Day 180
- Arm D: 400-mg LY3819469, dosed at randomization, placebo at Day 180
- Arm E: placebo, doses at randomization and Day 180

Brief Summary:

The purpose of this study is to measure difference in percent change from baseline in timeaveraged Lp(a) on over Days 60-180 with LY3819469 versus placebo in participants with elevated Lp(a).

Study details include:

- The study duration will be up to 20 months.
- The treatment duration will include doses at the randomization visit and at Day 180.

Study Population:

The study will include adults at least 40 years old. People in the study who are on particular medicines should stay on the same doses for the whole study. People who have had a major illness or surgery in the 3 months prior to the study will not participate. People who have certain abnormal laboratory values will not be included.

Number of Participants:

Approximately 254 participants will be randomly assigned to study intervention.

Intervention Groups and Duration:

All participants will receive a subcutaneous injection at the randomization visit and at Day 180 (Visit 7). LY3819469 is formulated at a concentration of 160 mg/mL.

	Arm A	Arm B	Arm C	Arm D	Arm E
Intervention Name	LY3819469	LY3819469	LY3819469	LY3819469 and Placebo	Placebo ^a
Dosage #1					
LY3819469 Solution (160mg/mL)	16 mg (0.1 mL)	96 mg (0.6 mL)	400 mg (2.5 mL)	400 mg (2.5 mL)	_
Placebo (0.9% sodium chloride solution for injection)	_	_	_	_	Placebo ^a
Dosage #2					
LY3819469 Solution (160mg/mL)	16 mg (0.1 mL)	96 mg (0.6 mL)	400 mg (2.5 mL)	_	_
Placebo (0.9% sodium chloride solution for injection)	_	_	_	Placebo ^b	Placebo ^a
Route of Administration	SC injection	SC injection	SC injection	SC injection	SC injection
Authorized as defined by EU Clinical Trial Regulation	Not authorized in EU	Not authorized in EU	Not authorized in EU	Not authorized in EU	Not authorized in EU

Abbreviations: EU = European Union; SC = subcutaneous.

- ^a Participants in Arm E will be randomly assigned so that each dose cohort will have a matching placebo cohort that receives the same dose volume to maintain the study blind.
- ^b Participants in Arm D will receive a 2.5-ml placebo dose at Day 180 (Visit 7).

Ethical Considerations of Benefit/Risk:

Based on current information, the study medicine treatment is believed to have more benefits than risks.

Data Monitoring Committee: No

1.2. Schema

1.3. Schedule of Activities (SoA)

Period I - Optional Prescreening: The study includes an optional prescreening visit (Visit 601) as a simple way for sites to determine whether participants meet Lp(a) criteria, as assessed by a central laboratory assessment, before the full screening activities are initiated at Visit 1. If the participant has not had Lp(a) measured before or is unknown, the prescreening visit should be completed. The prescreening visit can be conducted at the study site, or remotely, for example, at a mobile healthcare or alternate laboratory. The prescreening activities will be described in an appropriate informed consent form (ICF). Informed consent for the prescreening activities will be obtained, a participant identification number will be assigned, and sample for the Lp(a) prescreening laboratory test will be obtained. The optional prescreening visit can be repeated 1 time (no more) per participant if the investigator believes the participant would meet criteria at a later time, with a minimum of 4 weeks between visits. Repeated sampling in the prescreening is opted for, central laboratory testing for Lp(a) is still required as part of the screening procedures conducted at Visit 1. Participants with Lp(a) <175 nmol/L at Visit 1 will not be eligible for enrollment, despite their values in prescreening. A prescreening visit occurring longer or shorter than 21 days (3 weeks) from screening will not be considered a protocol deviation.

Period II - Screening: Visit 1 procedures may be conducted over more than 1 day as long as all activities are completed prior to Visit 2.

Period III - Treatment and Assessment Period: All procedures (screening and baseline) need to be completed prior to the first dose of study intervention. For an early discontinuation (ED) from the study intervention that occurs before the last visit in treatment period, see the activities listed for ED in this table.

	Period I - Pre- Screening	Period II - Screening			Per	riod I	II T	reatm		Participants are required to fast before Visits 1-12. See Section 5.3.1. If a participant arrives not fasted, schedule the laboratory draw for another date.					
Visit number	601	1	2	3	4	5	6	7	8	9	10	11	12	ED	
Days from randomization	≤42	≤21		15	30	60	120	180	210	240	300	360	540		Visit 1 procedures may be conducted over more than 1 day if all activities are completed within the allowable visit tolerance.
Visit interval tolerance (days)	See Section 1.3	_		±3	±3	±3	±7	±7	±7	±7	±7	±7	±14		
Prescreening informed consent	Х														
Informed consent		Х													The ICF must be signed before any protocol-specific tests or procedures are performed. See Appendix 10.1.3 for additional details.
Inclusion and exclusion criteria, review and confirm		Х	X												Inclusion and exclusion criteria should be confirmed-prior to drug assignment and administration of first dose of study intervention.
Ascertainment of high risk for cardiovascular events		Х													High risk for cardiovascular events will be defined as CAD, stroke, or peripheral artery disease, or ASCVD risk equivalents (familial hypercholesterolemia or type 2 diabetes)
Demographics		Х													Includes year of birth, sex, ethnicity (where permissible), and race.
Preexisting conditions and medical history, including relevant surgical history		X													All conditions ongoing and relevant past surgical and medical history should be collected.

	Period I - Pre- Screening	Period II - Screening			Per	riod I	II T	reatm		Participants are required to fast before Visits 1-12. See Section 5.3.1. If a participant arrives not fasted, schedule the laboratory draw for another date.					
Visit number	601	1	2	3	4	5	6	7	8	9	10	11	12	ED	
Days from randomization	≤42	≤21		15	30	60	120	180	210	240	300	360	540		Visit 1 procedures may be conducted over more than 1 day if all activities are completed within the allowable visit tolerance.
Visit interval tolerance (days)	See Section 1.3	—		±3	±3	±3	±7	±7	±7	±7	±7	±7	±14		
Prespecified medical history (indication and history of interest)		Х													Prespecified medical history includes history of cardiovascular events.
Prior treatments for indication		Х													Relevant prior therapies include, but are not limited to, lipid-lowering medications.
Substance use (alcohol, caffeine, and tobacco use)		Х						Х				Х	Х		
Concomitant medications		Х	Х	Х	Х	X	Х	Х	Х	Х	Х	Х	Х	Х	Additional data will be collected for medications of interest.
AEs	Х	Х	X	Х	X	X	Х	х	Х	Х	Х	Х	х	Х	Any events that occur after signing the informed consent are considered AEs as defined (Appendix 10.3). Additional data are collected for certain AEs.
Physical Evaluation															
Height		Х													Participant should remove shoes.
Weight		X	Χ					Х				Х	Х	Х	Participant should remove shoes.

	Period I - Pre- Screening	Period II - Screening			Per	riod I	II T	reatm	Participants are required to fast before Visits 1-12. See Section 5.3.1. If a participant arrives not fasted, schedule the laboratory draw for another date.						
Visit number	601	1	2	3	4	5	6	7	8	9	10	11	12	ED	
Days from randomization	≤42	≤21		15	30	60	120	180	210	240	300	360	540		Visit 1 procedures may be conducted over more than 1 day if all activities are completed within the allowable visit tolerance.
Visit interval tolerance (days)	See Section 1.3	—		±3	±3	±3	±7	±7	±7	±7	±7	±7	±14		
Vital signs		Х	x	X	X	Х	х	х	х	х	х	х	х	х	Includes pulse rate and blood pressure measured after participant has been sitting at least 5 minutes and before ECG tracing and collection of blood samples for laboratory testing.
Physical examination		Х											х	Х	The physical examination is performed (excludes pelvic, rectal, and breast examinations unless clinically indicated).
Symptom- directed physical assessment								Х							Symptom-directed physical assessment will be conducted at the discretion of the PI or qualified personnel, per local regulations, as indicated based on participant status and standard of care.
12-Lead ECG (local)		Х						X				X	X	X	Collect single, local ECG prior to collection of blood samples for laboratory testing, including PK samples. Participants should be supine for approximately 5 to 10 minutes before ECG collections and remain supine but awake during the ECG collection. ECGs may be repeated at the PI's discretion at any visit. See Section 8.2.1.

	Period I - Pre- Screening	Period II - Screening			Pei	riod I	11 T	reatmo		Participants are required to fast before Visits 1-12. See Section 5.3.1. If a participant arrives not fasted, schedule the laboratory draw for another date.					
Visit number	601	1	2	3	4	5	6	7	8	9	10	11	12	ED	
Days from randomization	≤42	≤21	_	15	30	60	120	180	210	240	300	360	540		Visit 1 procedures may be conducted over more than 1 day if all activities are completed within the allowable visit tolerance.
Visit interval tolerance (days)	See Section 1.3			±3	±3	±3	±7	±7	±7	±7	±7	±7	±14		
Laboratory Tests and Sample Collections															
Hematology		Х			Х	Х		Х	Х	Х		Х	Х		
Clinical chemistry		Х	Х	Х	Х	Х		Х	Х	Х		Х	Х	Х	
Lipid panel		Х	Х			Х		Х		Х		Х	Х	Х	
Urinalysis		Х				Х		Х		Х		Х	Х	Х	
UACR		Х				Х		Х		Х		Х	Х	Х	
Serum pregnancy		Х													Females only.
FSH		Х													Optional; performed as needed to confirm postmenopausal status. See Appendix 10.4.
TSH		Х													
HbA1c		Х						Х				Х	Х	Х	
Lp(a)	Х	Х	Х	Х	Х	Х	Х	Х	Х	Х	Х	Х	Х	Х	
ApoB		Х	Χ			Х	Х	Х	Χ	Х	Х	Х	Х	Х	
hsCRP		Х	Х			Х	Х	Х	Х	Х	Х	Х	Х	Х	
HIV screening test		Х													

	Period I - Pre- Screening	Period II - Screening			Per	riod I	II T	reatm		Participants are required to fast before Visits 1-12. See Section 5.3.1. If a participant arrives not fasted, schedule the laboratory draw for another date.					
Visit number	601	1	2	3	4	5	6	7	8	9	10	11	12	ED	
Days from randomization	≤42	≤21		15	30	60	120	180	210	240	300	360	540		Visit 1 procedures may be conducted over more than 1 day if all activities are completed within the allowable visit tolerance.
Visit interval tolerance (days)	See Section 1.3	—		±3	±3	±3	±7	±7	±7	±7	±7	±7	±14		
HCV screening test		Х													If HCV antibody test is positive, it must be followed by an HCV RNA test. See Section 8.2.5.
HBV screening test		Х													If HBsAg is negative and HBcAb is positive, further testing with HBV DNA is required. If the screening HBV DNA is negative, the participant is not excluded. See Section 8.2.4.
eGFR		Х				Х		Х		Х		Х	Х	Х	Calculated using CKD-EPI method.
Postdose PK sample			x					х							 Visit 2: Collect 2 samples. 0.5 hours postdose 4-9 hours postdose (minimum 2 hours) Visit 7: Collect 1 sample. 1. 24-36 hours postdose, will require participant to return 1 day after Visit 7.
Immunogenicity (ADA)			Р	Х	Х		Х	Р		Х		Х	Х	Х	Visit 2 and 7 will be collected predose.
PK sample for immunogenicity				X	X		X	Р		x		X	X	X	Collect a time-matched PK sample for all scheduled and unscheduled immunogenicity samples. Visit 7 will be collected predose.

	Period I - Pre- Screening	Period II - Screening			Per	iod II	(I T)	reatme		Participants are required to fast before Visits 1-12. See Section 5.3.1. If a participant arrives not fasted, schedule the laboratory draw for another date.					
Visit number	601	1	2	3	4	5	6	7	8	9	10	11	12	ED	
Days from randomization	≤42	≤21		15	30	60	120	180	210	240	300	360	540		Visit 1 procedures may be conducted over more than 1 day if all activities are completed within the allowable visit tolerance.
Visit interval tolerance (days)	See Section 1.3	—		±3	±3	±3	±7	±7	±7	±7	±7	±7	±14		
Stored Samples (On dosing days, collect samples before dosing	
Optional genetics sample			X												Sample can be obtained at or after the specified visit. See Appendix 10.5.
Exploratory biomarker samples			X			X		Х		Х		Х	х		
Randomization and Dosing															
Register visit with IWRS		X	X	X	X	X	X	Х	Х	Х	Х	Х	Х	Х	Unscheduled visits are not required to be registered in IWRS.
Randomization via IWRS			X												
Dispense study intervention via IWRS			X					X							
Administer study intervention			X					Х							

Abbreviations: ACC/AHA = American College of Cardiology/American Heart Association; ADA = anti-drug antibody; AE = adverse event; ApoB = apolipoprotein b; ASCVD = atherosclerotic cardiovascular disease; CAD = coronary artery disease; CKD-EPI = Chronic Kidney Disease Epidemiology Collaboration; DNA = deoxyribonucleic acid; ECG = electrocardiogram; ED = early discontinuation; eGFR = estimated glomerular filtration rate; FSH = follicle-stimulating hormone; HbA1c = hemoglobin A1c; HBcAb = hepatitis B core antibody; HBsAg = hepatitis B surface antigen; HBV = hepatitis B virus; HCV = hepatitis C virus; HIV = human immunodeficiency virus; hsCRP = high-sensitivity C-reactive protein; ICF = informed consent form; IWRS = Interactive Web-Response System; Lp(a) = Lipoprotein(a); P = predose; PI = principal investigator; PK = pharmacokinetic; RNA = ribonucleic acid; TSH = thyroid stimulating hormone; UACR = urine albumin creatinine ratio.

2. Introduction

LY3819469 is a novel Dicer-substrate small interfering ribonucleic acid (siRNA) oligonucleotide designed to reduce the levels of *LPA* mRNA and apolipoprotein(a) (Apo[a]) expression and thereby to decrease lipoprotein(a) (Lp[a]). LY3819469 is being developed to reduce the risk of cardiovascular events in patients with or at high risk of atherosclerotic cardiovascular disease (ASCVD) and high levels of Lp(a)

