## 7.1. Discontinuation of Study Intervention

When necessary, a participant may be permanently discontinued from study intervention. If so, the participant will remain in the study and follow procedures for remaining study visits, as shown in the SoA.

A participant should be permanently discontinued from study intervention if

- the participant becomes pregnant during the study
- in the opinion of the investigator, the participant should permanently discontinue the study intervention for safety reasons
- if the investigator determines that a systemic hypersensitivity reaction has occurred related to study intervention administration, the participant may be permanently discontinued from the study intervention, and the sponsor's designated medical monitor should be notified. If the investigator is uncertain about whether a systemic hypersensitivity reaction has occurred and whether discontinuation of study intervention is warranted, the investigator may consult the sponsor
- the participant has an AE or an SAE or a clinically significant change in a laboratory value that, in the opinion of the investigator, merits discontinuation of study intervention and appropriate measures being taken
- if the participant experiences a hepatic event or liver test abnormality as specified in the liver chemistry stopping criteria (see Section 7.1.1), and
- HBV or HCV: The participant tests positive for HBV DNA (see Section 8.2.4) or tests positive for HCV RNA (Section 8.2.5).

Note: The HBV DNA result is to be confirmed if initial positive test result is positive but below the level of quantification. Prior to discontinuation of any immunomodulatory and/or immunosuppressive therapy, including study intervention, the participant is to be referred to, evaluated, and managed by a specialist physician with expertise in evaluation and management of viral hepatitis. The timing of discontinuation from study intervention relative to the initiation of any antiviral treatment for hepatitis is to be based on the recommendation of the consulting specialist physician, in conjunction with the investigator, and aligned with medical guidelines and standard of care.

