#### CONFIDENTIAL

A participant may withdraw from the study:

- at any time at the participant's own request
- at the request of the participant's designee (for example, parents or legal guardian)
- at the discretion of the investigator for safety, behavioral, compliance, or administrative reasons
- if enrolled in any other clinical study involving an investigational product, or enrolled in any other type of medical research judged not to be scientifically or medically compatible with this study

At the time of discontinuing from the study, if possible, the participant will complete procedures for an early discontinuation (ED) visit, as shown in the SoA. If the participant has not already discontinued the study intervention, the participant will be permanently discontinued from the study intervention at the time of the decision to discontinue the study.

If the participant withdraws consent for disclosure of future information, the sponsor may retain and continue to use any data collected before such a withdrawal of consent. If a participant withdraws from the study, the participant may request destruction of any samples taken and not tested, and the investigator must document this in the site study records.

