#### **Comprehensive hepatic evaluation**

If a participant with baseline results of	develops the following elevations:
ALT or AST <1.5x ULN	ALT or AST $\geq$ 3x ULN with hepatic signs/symptoms ^a , or
	ALT or AST ≥5x ULN
ALP <1.5x ULN	ALP ≥3x ULN
TBL <1.5x ULN	TBL $\geq 2x$ ULN (except for patients with Gilbert's syndrome)
ALT or AST ≥1.5x ULN	ALT or AST $\geq 2x$ baseline with hepatic signs/symptoms ^a , or
	ALT or AST ≥3x baseline
ALP ≥1.5x ULN	$ALP \ge 2x$ baseline
TBL ≥1.5x ULN	TBL $\geq 2x$ baseline (except for patients with Gilbert's syndrome)

A comprehensive evaluation should be performed to search for possible causes of liver injury if one or more of these conditions occur:

Abbreviations: ALP = alkaline phosphatase; ALT = alanine aminotransferase; AST = aspartate aminotransferase; TBL = total bilirubin; ULN= upper limit of normal.

^a Hepatic signs/symptoms are severe fatigue, nausea, vomiting, right upper quadrant abdominal pain, fever, rash, and/or eosinophilia >5%.

At a minimum, this evaluation should include physical examination and a thorough medical history, as outlined above, as well as tests for prothrombin time, international normalized ratio (PT-INR); tests for viral hepatitis A, B, C, or E; tests for autoimmune hepatitis; and an abdominal imaging study (for example, ultrasound or computerized tomography [CT] scan).

Based on the patient's history and initial results, further testing should be considered in consultation with the Lilly-designated medical monitor, including tests for hepatitis D virus (HDV), cytomegalovirus (CMV), Epstein-Barr virus (EBV), acetaminophen levels, acetaminophen protein adducts, urine toxicology screen, Wilson's disease, blood alcohol levels, urinary ethyl glucuronide, and blood phosphatidylethanol. Based on the circumstances and the investigator's assessment of the participant's clinical condition, the investigator should consider referring the participant for a hepatologist or gastroenterologist consultation, magnetic resonance

cholangiopancreatography (MRCP), endoscopic retrograde cholangiopancreatography (ERCP), cardiac echocardiogram, or a liver biopsy.

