1.3) Change from	All randomized	The last scheduled nonmissing	Postbaseline will be defined
Last Baseline for	participants who are	assessment recorded prior to the	as above (1.1). Only
Labs, Vital Signs	exposed to at least 1 dose	date of first dose of study	scheduled visits will be
(FAS)	of study drug and have a	treatment during the baseline	included. The early
	baseline and at least	period defined above (1.1).	discontinuation visits are
	1 postbaseline		considered scheduled visits.
	observation		
Immunogenicity	All randomized	Baseline is defined as predose	Postbaseline will be defined
(FAS)	participants who are	collection at Visit 2.	as above (1.1). Only
	exposed to at least 1 dose		scheduled visits will be
	of study drug and have a		included. The early
	baseline and at least		discontinuation visits are
	1 postbaseline		considered scheduled visits.
	observation		

 Table EZEB.4.3.
 Baseline and Postbaseline Definitions for Safety Analyses

Abbreviation: FAS = full analysis set.

Note: For the continuous analysis of clinical laboratory tests, unscheduled measurements are excluded from analysis to reduce bias. The early discontinuation visits are considered scheduled visits.

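### Hematology is the only recurring routine safety laboratory panel with no draw at the early discontinuation (ED) visit, and no reason is given

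*Protocol*

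**What the plan says.** The laboratory block of the Schedule of Activities (SoA, protocol Section 1.3) is headed "Laboratory Tests and Sample Collections". Its Hematology row is marked at screening and at Days 30, 60, 180, 210, 240, 360 and 540. The ED and comment cells are empty. Every other recurring safety laboratory row (clinical chemistry, lipid panel, urinalysis, UACR, HbA1c, eGFR) carries an ED mark.

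Protocol Section 7.2 covers people leaving the study: if possible, "the participant will complete procedures for an early discontinuation (ED) visit, as shown in the SoA". Section 7.1 covers people who stop study intervention only: "the participant will remain in the study and follow procedures for remaining study visits". The SoA introduction ties the ED column to a different event: "For an early discontinuation (ED) from the study intervention that occurs before the last visit in treatment period". The two triggers should be reconciled. The count below uses Section 7.2, because Section 7.1 keeps drug-only discontinuers on the scheduled hematology draws.

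On analysis, the note to SAP Table EZEB.4.3 says: "The early discontinuation visits are considered scheduled visits". The same note removes unscheduled measurements from continuous laboratory analyses. SAP Section 4.1, however, drops ED data that do not match the planned collection schedule from MMRM, ANCOVA and logistic regression. Treatment-emergent laboratory tables use all scheduled and unscheduled post-baseline values (Section 4.1; Table EZEB.4.3, row 1.2). The shift table includes unplanned values and has a missing category (Section 4.8.6).

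**The concern.** The ED visit is the last planned chance to observe someone who leaves. Blood is already drawn there for the other recurring safety panels, so an unexplained blank for hematology looks like an oversight. The protocol says the sample size was chosen to give enough safety data (Section 9.5), and the human data it describes come from single doses, whereas this trial gives up to two.

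Without an exit count, a change in blood counts between the last scheduled draw and exit goes unrecorded unless an investigator orders a test. Such a test is allowed (Appendix 10.2) but not required by the SoA. If it is done, the value reaches the treatment-emergent and shift tables but not the continuous laboratory analyses.

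**Working it through.** **The plan's own figures.** Inputs are in protocol Section 9.5 and SAP Section 5: 254 randomized 1:2:2:2:2, 15% dropout.
- 16-mg arm: 254 × 1/9 × 0.85 = 23.99, stated as 24.
- Each other arm: 254 × 2/9 × 0.85 = 47.98, stated as 48.
- Leavers: 254 × 0.15 = 38.1. Check: 254 − (24 + 4 × 48) = 254 − 216 = 38.

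The completer figures reproduce. Thirty-eight is a ceiling for missing exit counts, because not every leaver will attend an ED visit.

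**The grid.** Hematology has 8 marks and none at ED. Clinical chemistry has 11 (Visits 1, 2, 3, 4, 5, 7, 8, 9, 11, 12 and ED). The two rows have the same number of cells, so a column shift is unlikely.

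**Age of the last scheduled count at exit.** Post-dose draws fall on Days 30, 60, 180, 210, 240, 360 and 540. Starting from Day 0, the gaps are 30, 30, 120, 30, 30, 120 and 180 days. The longest are Days 60–180 and 240–360 (120 days each) and Days 360–540 (180 days). The documents do not give exit timing, so I assume uniform exit over two horizons. Mean age is the sum of squared gaps divided by twice the horizon.

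| | Exits over 540 days | All exits by Day 180 |
|---|---|---|
| Sum of squared gaps | 64,800 | 900 + 900 + 14,400 = 16,200 |
| Mean age | 64,800 / 1,080 = 60 days | 16,200 / 360 = 45 days |
| Share over 90 days old | (30 + 30 + 90) / 540 = 27.8% | 30 / 180 = 16.7% |
| Leavers before Day 30 | 38.1 × 30/540 = 2.1 | 38.1 × 30/180 = 6.4 |

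With the ±3-day window at Visit 4 (Day 27 to 33), the last row becomes 1.9–2.3 and 5.7–7.0. Age in the first 30 days is counted from Day 0. The preceding count is the screening one, up to 21 days earlier, so the means are slightly low.

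**What reaches the tables.** Row 1.2 of Table EZEB.4.3 needs a post-baseline observation. The 2 to 6 leavers before Day 30 would, without an unscheduled count, leave the treatment-emergent hematology denominator; the shift table has a missing category for them. The other 32 to 36 have at least one scheduled post-dose count, provided they attended their visits.

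**The case against.** The case against is that this is one blank cell with little consequence, and much of it stands.

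- A reader might infer that early leavers in general fall out of the hematology tables. The SAP does not work that way. Anyone with one post-dose count, scheduled or not, contributes to the treatment-emergent and shift tables.
- A reader might infer bias toward no signal. The documents do not show it. No difference in exits between arms is given, and the protocol reports no notable adverse effects in toxicology or Phase 1 (Sections 2.2.4 and 2.3.1). Loss of late information is plausible; a direction of bias is not established.
- A reader might infer that eosinophils, which count among the protocol's hepatic signs at more than 5%, cannot be obtained for a leaver. Appendix 10.6 lists a hepatic hematology panel with eosinophils, so they are available through the hepatic work-up. They are only absent from the routine ED draw.
- Appendix 10.3.4 obliges the investigator to arrange medically indicated extra tests for adverse events. Chemistry without hematology also occurs at Visits 2 and 3, so unpaired sampling is not peculiar to ED.
- The ED visit takes place only if possible, and people lost to follow-up have no exit sample of any kind.
- Alignment rules out a column shift but not a dropped mark. In the repeated table header above this row, a dash shown elsewhere in the visit-tolerance line is missing from the extracted text.

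What these points leave open is why hematology alone has no routine ED draw. Discretionary or event-driven testing does not give every attending leaver an exit count.

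**Conclusion.** The point holds as an unexplained gap in the SoA that is cheap to close. It leaves at most about 38 of 254 participants without a scheduled exit blood count. For most of them the loss is the last interval before exit: a mean of 45 to 60 days, and at worst about 120 or 180 days depending on when they leave. About 2 to 6 would have no scheduled post-dose count.

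These sizes rest on the planned 15% dropout, on uniform exit over 180 or 540 days, and on attendance at scheduled visits. Exits clustered soon after the first dose would raise the number with no post-dose count. The primary endpoint, sample size and power are untouched. The finding also depends on the ED cell being blank on the protocol page itself.

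A reader might also conclude that marking the cell is enough and the SAP can stay as it is. The documents do not support that: SAP Section 4.1 and Table EZEB.4.3 treat ED data differently, so the use of an added count in the continuous analyses would remain unclear.

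**What to change.** 1. Check the Hematology ED cell against the protocol page. If it is blank, mark it in SoA Section 1.3, with the sample taken alongside the existing ED chemistry draw. If the omission is deliberate, state the reason.
2. Add one sentence to the SAP that reconciles Section 4.1 with the note to Table EZEB.4.3. It should say whether, and at which visit, ED laboratory values enter the change-from-baseline summaries and the MMRM or ANCOVA models.

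The cost is one extra tube at an existing draw for at most about 38 participants, a one-cell SoA change and one SAP sentence. There is no extra visit.
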